15. REGULATIONS ON CLINICAL TRIAL PROTOCOL DEVIATIONS AND CLINICAL TRIAL PROTOCOL AMENDMENT

Study protocol deviation refers to a case where the requirements of the Clinical Trial Protocol are not followed intentionally or unintentionally.

All protocol deviations should be reported to the sponsor as protocol deviations, and all protocol deviations should be reported in the protocol deviation form and monitoring report, including the date and reason of protocol deviation. The investigator should also report the protocol deviation to

the hospital's medical device clinical trial management department according to the hospital's procedures and regulations, and report to EC through the department.

If a protocol amendment occurs, the Sponsor or designated person should submit a summary of changes of the study protocol to the Investigator, regulatory authority, and the Ethics Committee, etc. according to the relevant laws and regulations. All significant amendments must be approved by the EC and regulatory authorities (if required) prior to implementation of any changes to study procedures.

An amendment is regarded substantial when they are likely to have a significant impact on:

- The safety or physical or mental integrity of the subjects;
- Scientific value of trial;
- Conduct or management of the trial;
- Quality or safety of investigational medical device specified in the trial.

16. DIRECT ACCESS TO SOURCE DATA AND DOCUMENTS

Source data refers to the original records of clinical findings, observations and other activities during clinical trials, as well as all information in their approved copies, which can be used for clinical trial redesign and evaluation. A source document is a printed, paper or electronic file containing source data, among others.

The investigator should maintain and retain information in the subject's medical records and other study-related documents (source documents). The Investigator should allow the monitors and auditorsinspectors to review the following information, including but not limited to:

- Confirm the medical history/physical condition of the study subject who meets the inclusion criteria of the study protocol before participating in this study;
- Medical record documenting the informed consent process;
- Description of operation of investigational product;
- All inspection results and follow-up;
- Dated and signed inspection printouts or reports;
- Description of AE and follow-up of AE (event description, severity, onset date, duration, correlation with the study device, study procedures, outcome and treatment of AE, concomitant medication/procedure when AE occurs);
- Description of the device defects
- Conditions of study subjects when they complete the study or withdraw from the study.

Appropriate source documents must be available for reviewing during the monitoring visit. The Sponsor expects that the study coordinator and/or investigator will also be available for questions during monitoring visits.

17. FINANCES AND INSURANCE

See the relevant study contract and insurance documents.

18. CONTENTS TO BE COVERED IN THE CLINICAL TRIAL PROTOCOL

According to regulatory requirements, the clinical trial report will include the following contents:

The clinical trial report shall be consistent with the protocol, mainly including:

- 1) General Information;
- 2) SYNOPSIS;
- 3) Introduction;
- 4) Objective of Clinical Trial;
- 5) Clinical Trial Method;
- 6) Contents of Clinical Trial;
- 7) General Data of Clinical Trial;
- 8) Diagnosis and treatment methods of investigational medical devices;
- 9) Statistical analysis methods and evaluation methods adopted;
- 10) Clinical Evaluation Criteria;
- 11) The organizational structure of clinical trial;
- 12) Ethical description;
- 13) Results of the clinical trial;
- 14) Adverse events found in clinical trial and corresponding treatment;
- 15) Analysis and discussion of clinical trial results, especially indications, scope of application, contraindications and precautions;
- 16) Clinical trial conclusion;
- 17) Problems in existence and suggestions for improvement;
- 18) List of study personnel;
- 19) Other Situations to be Explained;
- 20) Clinical trial summary of each sub-site.

19. PRINCIPLES OF CONFIDENTIALITY

The personal data of subjects participating in the trial shall be kept confidential. However, the Ethics Committee, the sponsor, the health regulatory authorities and their authorized representatives may review the personal data of subjects participating in the trial according to the specified procedures.

Subject confidentiality will be maintained throughout the clinical study in a way that ensures the information can always be tracked back to the source data. For this purpose, a unique subject identification code (site number and subject number) will be used to identify all data reported for each subject. So long as the data is kept strictly confidential and that the privacy of the subject is ensured to be protected, the data related to this study may be available to third parties (for example, under the audit of regulatory authority).

20. CONVENTION ON PUBLICATION OF TRIAL RESULTS

At the end of the study, a multicenter clinical trial manuscript will be prepared and published in a reputable scientific journal as needed. The publication of the principal results from any single-site experience within the study is not allowed until the preparation and publication of the multi-center trial results. Exceptions, such as pre-specified and non-pre-specified analyses of other endpoints, or such secondary analyses and proposed additional investigational studies, require prior approval by the sponsor. For purposes of timely abstract presentation and publication, secondary publications will be delegated to the appropriate principal authors, and final analyses and manuscript review for all multi-center trial data will require the approval of the sponsor.

21. RESPONSIBILITIES UNDERTAKEN BY DIFFERENT PARTIES

21.1. Responsibilities of the Sponsor

- 1) The Sponsor is responsible for the initiation, application, organization and monitoring of clinical trial.
- 2) The Sponsor is responsible for the organization to establish and modify the investigator's brochure, clinical trial protocol, informed consent form, Case Report Form, relevant standard operating procedure and other relevant documents, carry out the training required for the clinical trial, and provide these documents to the investigators before the study starts.
- 3) The Sponsor should select the qualified trial institution and investigators.
- 4) The Sponsor should sign a written agreement with the clinical trial institution and the investigator regarding the clinical trial.
- 5) The Sponsor should provide qualified study product according to the regulatory requirements. The Sponsor should be responsible for the safety of investigational medical device in the clinical trial. The AE, SAE, and the device complaint that may cause an SAE should be collected and reported in accordance with the provisions.
- 6) The Sponsor should inform the regulatory authority at every level when the Sponsor decides to suspend or terminate the clinical trial or at the end of the study.
- 7) The Sponsor should ensure the investigator conducts the study strictly in compliance with the clinical trial protocol, corrects the protocol deviations in a timely way, and reserves the rights to

report, to the regulatory authority, any of issues related to this.

- 8) The Sponsor should bear the treatment cost and relevant economic compensation for the clinical trial-related injury or death of subjects, except for damages due to the fault of medical institution and medical staff in the diagnosis and treatment.
- 9) The Sponsor should select qualified monitors for monitoring and organizing any inspections, as appropriate.

21.2. Responsibilities of Clinical Trial Institution and Investigator

- 1) The clinical trial institution should evaluate the relevant resources according to the features of investigational medical device prior to the clinical trial, to decide whether to participate in this clinical trial.
- 2) The clinical trial institution should properly keep the records and documents of clinical trial according to the agreement with the Sponsor.
- 3) Make sure that the investigators responsible for the clinical trial have the qualification in accordance with the requirements of related laws and regulations.
- 4) The administrative department of the clinical trial institution conducting the medical device clinical trial should cooperate with the Sponsor to apply to the Ethics Committee and submit the relevant documents prior to the clinical trial according to requirements.
- 5) The investigator should ensure that the relevant workers participating in the trial have the enough resources and proper training and keep the training related documents.
- 6) The investigator should ensure to use the investigational medical device only for the subjects of this clinical trial.
- 7) The investigator may not charge subjects any fees for participating in the study.
- 8) The investigator should strictly follow the clinical trial protocol, with the exception of emergency circumstances when the patient faces the direct risk and needs immediate clinical measures, which can be reported later in a written form.
- 9) The investigator is responsible for recruiting the subjects, communicating with the patient or its legal representative before signing the informed consent.
- 10) The investigator should protect the rights, safety and health of the subjects.
- 11) In case of an AE occurring in the clinical trial, the investigator should protect the safety of the subjects and timely report the event to the regulatory authority.
- 12) The investigator should record all AEs occurring and device deficiencies found in the process of clinical trial, work with the Sponsor to analyze the causes of the events, generate the written analysis report, present the comments on the continuation, discontinuation or termination of the trial, and report to the Ethics Committee by the administrative department for clinical trial of

medical device of clinical trial institution for review.

- 13) The investigator should make sure that the clinical trial data is accurately, completely, clearly and timely recorded in the Case Report Form.
- 14) The clinical trial institution and investigator should make sure that the data, documents and records generated in the clinical trial are timely, true, accurate, clear, and attributable.
- 15) The clinical trial institution and investigator should accept and cooperate with the monitoring and audit of the Sponsor, the supervision of the Ethics Committee, and the inspection of the Food and Drug Administration, competent department of health and family planning, etc., and provide all required records related to the trial.
- 16) If the clinical trial needs to be suspended or terminated, the subjects should be informed accordingly. It should be ensured that the subjects receive the proper care and follow-up. The clinical trial institution and investigator should also report this in accordance with the regulations and provide a detailed written explanation. The relevant report should be submitted to the local Food and Drug Administration at the provincial, autonomous regional and municipal level, if necessary.
- 17) The clinical trial institution and investigator reserve the rights to report to the regulatory authority at every level when the Sponsor violates relevant laws and regulations.
- 18) The investigator should complete all records and reports at the end of clinical trial. The investigator should also ensure that the received investigational medical devices are properly handled and recorded according to the requirements.

APPENDIX 1: STUDY DEVICES CODE LIST

Investigation Product	Model	Description
	NWC2CN1N	NeuWave Certus™ Microwave Ablation System
	CTBKT1	CT Bed Rail PDM Mounting Bracket, Standard (Applicable to GE, Philips)
	CTBKT2	CT Bed Rail PDM Mounting Bracket, D68 X W585 Standard (Applicable to Siemens)
	CTBKT3	CT Bed Rail PDM Mounting Bracket, D48 X W656 Standard (Applicable to Toshiba)
	CTBKT4	CT Bed Rail PDM Mounting Bracket, D88 X W645 (Siemens Alt)
	CTBKT5	CT Bed Rail Mount, Flat
	LN15CN	NEUWAVE CERTUS LN Probe 15CM 17ga
	LN20CN	NEUWAVE CERTUS LN Probe 20CM 17ga
	LK15CN	NEUWAVE CERTUS LK Probe 15CM 17ga
	LK20CN	NEUWAVE CERTUS LK Probe 20CM 17ga
	LK15XTCN	NEUWAVE CERTUS LK XT Probe 15CM 15ga
	LK20XTCN	NEUWAVE CERTUS LK XT Probe 20CM 15ga
	PR15CN	NEUWAVE CERTUS PR Probe 15CM 17ga
	PR20CN	NEUWAVE CERTUS PR Probe 20CM 17ga
	PR15XTCN	NEUWAVE CERTUS PR XT Probe 15CM 15ga
	PR20XTCN	NEUWAVE CERTUS PR XT Probe 20CM 15ga
NOTE: These are collectively described as "study devices."		

## Revision History

Revision Number	Revision Date (DD/MMM/YYYY)	Reasons for Revision
Version 1.0	22/Mar/2022	NA

## Abbreviations

AE	Adverse Event
CI	Confidence Interval
CP	Conditional Power
CRF/e-CRF	Case Report Form / Electronic Case Report Form
CSR	Clinical Study Report
CT	Computed Tomography
DMC	Data Monitoring Committee
ECOG PS	Eastern Cooperative Oncology Group Performance Status
EORTC QLQ-C30	European Organisation for Research and Treatment of Cancer Quality of Life Questionnaire -Core 30
EORTC QLQ-LC13	European Organisation for Research and Treatment of Cancer Quality of Life Questionnaire -Lung Cancer-specific Module
FAS	Full Analysis Set
GGO	Ground Glass Opacity
ICF	Informed Consent Form
IRC	Independent Review Committee
KM	Kaplan-Meier
MedDRA	Medical Dictionary for Regulatory Activities
NMPA	National Medical Products Administration
MW	Microwave
NPRS	Numeric Pain Rating Scale
NSCLC	Non-small Cell Lung Cancer
OS	Overall Survival
PD	Progression of Disease
PFS	Progression-Free Survival
PG	Performance Goal
PI	Principle Investigator
PP	Per Protocol
PT	Preferred Term
QOL	Quality of Life
SAE	Serious Adverse Event
SAF	Safety Analysis Set
SAP	Statistical Analysis Plan
SE	Standard Error
SOC	System Organ Class

## **1 Study Overview**

### **1.1 Study Design**

This study is a single-arm, prospective, multicenter clinical trial with a performance goal (PG).

The study population includes adult subjects with non-small cell lung cancer (NSCLC) or oligometastatic lung tumors who plan to receive percutaneous microwave ablation. Individuals who have lung tumor(s) meeting the eligibility criteria of the study and sign the Informed Consent Form will be enrolled into this study.

Each enrolled subject will have his or her eligible lung tumor(s) ablated using the NeuWave Certus Microwave Ablation System (in conjunction with the NeuWave Certus Microwave Ablation Probes) in a single procedure. Subjects will be followed at 1, 3, 6, and 12 months after the initial microwave ablation procedure to evaluate the effectiveness and safety of percutaneous microwave ablation with the study device.

To provide study sites with an opportunity to get equal experience in the use of the Certus system, each study site will have two (2) subjects treated as part of a run-in phase. These subjects will only be included in the safety analysis set.

### **1.2 Study Objective**

The objective of this study is to evaluate the effectiveness and safety of the NeuWave Certus Microwave Ablation System and Accessories for percutaneous microwave ablation of non-small cell lung cancer and oligometastatic lung tumors.

### **1.3 Study Endpoints**

#### **1.3.1 Primary Endpoint**

Technical Efficacy Rate: Percentage of tumors that are completely covered by the ablation area without signs of pathological enhancement as assessed by lung enhanced CT at Visit 3 (i.e., 30 days $\pm$ 7 days after the first ablation).

#### **1.3.2 Secondary Endpoints**

- Secondary Efficacy Endpoints

- Technical Success Rate: Percentage of tumors that achieve A0 or A1 ablation classification determinations (i.e., complete tumor ablation with a surrounding margin) based on the lung CT immediately following the initial ablation procedure.
- A0 Ablation Rate: Percentage of tumors that achieve A0 ablation (i.e., the ablation zone covers the tumor completely and has a minimal margin of at least 5mm for secondary lung tumors and at least 10mm for primary lung tumors) based on the lung CT immediately following the initial ablation procedure.

Note: NSCLC are primary tumors and oligometastatic lung tumors are secondary.

- Re-Ablation Technical Success Rate: Percentage of tumors that achieve Technical Success in the lung CT immediately following the repeat ablation with the study device during the study.
- Local Tumor Progression: Local tumor progression and time to local tumor progression of any original-ablated tumor(s).
- Progression-Free Survival: Length of the time the subject is still alive after the original ablation procedure and with no evidence of any tumor progression (local, regional, or distant).
- Overall Survival: Length of time that the subject is still alive after the original ablation procedure within the study duration.
- Safety Endpoints
  - All AEs from the start of any ablation procedure (starting from the time of probe puncture on skin) to 30 days post-ablation or early discontinuation.
  - All SAEs from the start of ablation procedure through the end of the study or early discontinuation.
  - All device-related AEs, procedure-related AEs, device-related SAEs, and procedure-related SAEs from the start of ablation procedure through the end of the study or early discontinuation.

### 1.3.3 Exploratory Endpoints

- Patient-Reported Outcomes
  - Ablation-Procedure Related Pain: Compare the 1 day, 3 days, and 1-month post-ablation versus pre-ablation patient-reported pain levels using the Numeric Pain Rating Scale.
  - Quality of Life: Compare the patient's 1 month post-ablation, 6 months post-ablation, 12 months post-ablation to the pre-ablation Quality of Life scores using EORTC QLQ-C30 and Lung-specific QLQ-LC13.

- ECOG Performance Status: Patient functionality as measured by distribution of Eastern Cooperative Oncology Group (ECOG) classification scores over time.
- Ablation Procedure Related Indicators: Number and types of probes used, number of ablation cycles, ablation power, and ablation time.
- Length of Hospital Stay: The duration from the patient's completion of ablation procedure to discharge.
- Re-admission Rate: Percentage of unplanned hospital admission or re-admission due to an adverse event occurring within 30 days after any ablation procedure using the study device (i.e., the original ablation or a repeat ablation).

## **2 Treatment Assignment**

All enrolled subjects will undergo percutaneous microwave ablation with the NeuWave Certus Microwave Ablation System (in conjunction with NeuWave Certus Microwave Ablation Probes).

## **3 Randomization and Blinding Procedures**

This is a single-arm, open-label study. No randomization will occur.

The study team will be blinded to the summary results of the primary effectiveness endpoint until the database lock of the study primary analysis. Details of blinding procedures are documented in the blinded plan.

## **4 Interval Windows**

Interval windows are provided in the Schedule of Activities in Table 1 of the protocol. Data collected in Unscheduled Visit forms will be listed as such.

## **5 Levels of Significance**

In this study, the statistical power of 80% and the significance level of one-sided 0.025 are used for the sample size calculation based on the primary effectiveness endpoint (i.e. Technical Efficacy Rate) hypothesis testing.

## **6 Analysis Sets**

The analysis sets are defined as follows:

- The Full Analysis Set (FAS) is defined as all subjects who are enrolled in the study and received ablation power (excluding the run-in subjects).
- The Per Protocol (PP) set is defined as subjects in FAS without major protocol deviations that have great impact on the primary effectiveness endpoint.

- The Safety Analysis Set (SAF) includes all subjects who provide informed consent and have microwave ablation attempted with the NeuWave system (including the run-in subjects).
- Run-in Set includes all subjects who are enrolled in the study and enter the run-in phase.

The primary effectiveness endpoint will be analyzed on the FAS and PP. The analysis on the FAS is the primary analysis and the analysis on the PP set is the sensitivity analysis.

The secondary and exploratory effectiveness endpoints will be analyzed on the FAS.

All safety endpoints will be analyzed on the SAF. The AE summary table will be presented on the FAS and run-in set as well.

For subjects included in the run-in set, all baseline data, surgical information, and effectiveness data will be described as the continuous variable and categorical variable. No confidence interval (CI) will be provided. Only observed data will be analyzed and no missing data imputation rule will be applied to subjects in the run-in set.

The protocol deviations impacting the PP set will be reviewed and finalized during the data review meeting held prior to database lock of the primary analysis.

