 - (4) Post-ablation: After the ablation is completed, confirm the ablation procedure is completed using CT taken approximately 10 minutes after the ablation is completed and

determine whether the ablation lesion covers the tumor. If the ablation margin is not sufficient (i.e. Did not reach at least 5mm of safety margin for oligometastatic lung tumor or at least 1cm safety margin for NSCLC), the study physician should repeat the ablation to achieve an adequate ablation margin if the situation permits.

- Record ablation procedure details, including but not limited to the following:
 - Procedure date and time
 - Mode of anesthesia
 - Guidance method used
 - Anatomic location of ablated tumor
 - Number of ablation cycles
 - Ablation power and time
- Device count: all probe types and amounts.
- Intra-ablation Screening: For patients who meet the intra ablation exclusion criteria, they will be considered an intra-ablation screening failure, and will record:
 - Informed consent date
 - Demographic information (age, race, gender, and ethnicity)
 - Reason for screening failure
- Intra-ablation Stopping Criteria and Procedure:
 - During the ablation procedure, if the investigator should stop the procedure after probe puncture but before any microwave power emission to the subject's lung tumor, due to adverse events like severe bleeding/pneumothorax, or due to any other presenting conditions, the patient will be withdrawn from the study, recording the reason, and receive a follow-up period of 30 days after the procedure from the safety evaluation perspective. If the withdrawn subject reports a SAE, the subject will be followed until resolution of the event, a stable endpoint is reached, or until the event is appropriately explained.
 - For subjects with multiple tumors identified to be ablated during screening, if not all of the identified tumors receive ablation, the reason(s) for not ablating any of the identified tumors will be recorded. The subject will not be withdrawn from study. Further treatment on the non-ablated tumors will be based on sites' SOC (i.e., not using the study devices).
- The tumors that have been identified to be ablated during screening and receive ablation power during the initial ablation procedure will be regarded as "Target Tumor(s)". Only the "Target Tumor(s)" will undergo tumor level effectiveness evaluations (i.e., Technical

Success, Technical Efficacy, and Local Tumor Progression).

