7. The number and percentage of subjects who complete and do not complete the study and the specific reasons for not completing the study will be counted and calculated based on the patient level.

Note: Primary and secondary efficacy endpoints related to efficacy that are assessed by both the study physician (i.e., PI) and Independent Central Imaging Committee (IRC) as described in

Section 7.1, including Technical Efficacy Rate, Technical Success Rate, A0 Ablation Rate, Re-ablation Technical Success Rate, and Local Tumor Progression will be recorded.

- **Safety endpoints:**

The safety endpoints will be summarized in the safety set, where the safety data of subjects in the run-in period can be summarized separately from the rest of subjects. The number and percentage of subjects experiencing any adverse event (AE) and serious adverse event (SAE) will be summarized at the preferred term level of MedDRA. The severity of AEs and SAEs will be summarized. The AEs and SAEs will also be summarized according to the Society of Interventional Radiology (SIR) classification. Study device-related AEs, ablation procedure-related AEs, all SAEs, device-related SAEs, and ablation procedure-related SAEs will be summarized in a similar way. Besides, the incidence of the predefined AEs below will also be summarized and reported:

1. Pneumothorax (all and those requiring chest tube drainage)
2. Hemorrhages (all and those requiring treatment)
3. Post-ablation syndrome
4. Chest wall pain
5. Pleural Effusion (all and those requiring chest tube drainage)
6. Pneumonia
7. Pulmonary or pleural abscess
8. Other infections
9. Bronchopleural fistula

- **Three analyses in total are planned.**

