8.7. Selection Criteria and Rationale for Subjects Included in the Analysis

All subjects who met the inclusion and exclusion criteria are considered to meet the recruitment requirements.

The primary analysis of safety and effectiveness endpoints will be performed on the Full Analysis Set. Primary Effectiveness endpoint analyses will be repeated for the Per Protocol Set. The Safety Set will only be used for summarization of safety endpoints. Safety and effectiveness data collected on patients participating in the run-in phase may be summarized separately from the remaining patients.

Subgroup analysis will be conducted as needed and will be described in the SAP.

The analysis sets in this study are defined as follows:

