### **8.10.7 Safety Analyses**

Analyses will be performed at subject level on the SAF. The AE summary will be provided on the FAS and run-in set as well.

All AEs that occur on or post the initial ablation date or occurs before the initial ablation date and related (Unlikely, Possibly, Probably, or Causal) to the study device or study procedure will be presented.

AEs will be coded using MedDRA. The number of events and the number and percentage of subjects reporting AEs and SAEs will be summarized at the MedDRA system organ class and preferred term level. The severity of AEs and SAEs will be summarized. The AEs and SAEs will also be summarized according to the Society of Interventional Radiology (SIR) classification. Similar summaries will also be provided for AEs and SAEs related to the study device, AEs and SAEs related to the study procedure, and device deficiencies. Related events are those where the relationship is indicated as Unlikely, Possibly, Probably, or Causal by the PI. In addition, related events where the relationship is indicated as Possibly, Probably, or Causal will also be summarized. Summaries of all AEs and SAEs reported within the first 30 days after the initial ablation procedure and overall will be generated. The incidence of predefined AEs will also be summarized and reported, including pneumothorax (all and those requiring chest tube drainage), hemorrhage (all and those requiring treatment), post-ablation syndrome, chest wall pain, pleural effusion (all the those requiring chest tube drainage), pneumonia, pulmonary or pleural abscess, other infections, and bronchopleural fistula.

All AE/device deficiencies will be listed.

All abnormal laboratory tests and positive blood or urine pregnancy test results will be listed.

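### The additional AE summary on the FAS leaves out main-phase subjects stopped after probe puncture but before power, so it can understate main-phase complication rates (minor)

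*SAP*

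**What the plan says.** SAP 6 defines three sets that matter here.

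- **FAS:** "all subjects who are enrolled in the study and received ablation power (excluding the run-in subjects".
- **SAF:** "all subjects who provide informed consent and have microwave ablation attempted with the NeuWave system (including the run-in subjects".
- **Run-in set:** "Run-in Set includes all subjects who are enrolled in the study and enter the run-in phase".

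SAP 6 places all safety endpoints on the SAF. It then adds: "The AE summary table will be presented on the FAS and run-in set as well". SAP 8.10.7 repeats this: "The AE summary will be provided on the FAS and run-in set as well".

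Protocol 7.2.3 (Visit 2A, stopping criteria) foresees that a procedure may be stopped between probe puncture and the first power emission: "due to adverse events like severe bleeding/pneumothorax, or due to any other presenting conditions, the patient will be withdrawn from the study". Protocol 7.1.5 and 8.5 replace such a subject with a new one. Protocol 7.1.8 follows the stopped subject for safety for 30 days, starts AE reporting at skin puncture, and lists pneumothorax and hemorrhage among the AEs to be summarized.

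On the split by phase, Protocol 8.1 works inside the safety set: "the safety data of subjects in the run-in period can be summarized separately from the rest of subjects". Protocol 8.7 reads differently: "The primary analysis of safety and effectiveness endpoints will be performed on the Full Analysis Set".

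**The concern.** The two added AE tables look like a main-phase table and a run-in table, but their entry rules differ. The main-phase table requires power; the run-in table does not. The subjects lost from the main-phase table are not a random few. The protocol's own examples of why they leave are bleeding and pneumothorax, two of the complications that the study sets out to count.

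Protocol 7.1.3 gives the run-in a purpose, which is to reduce bias from the learning curve. The AE summary without run-in subjects is the one a reader would naturally take as the complication profile after that phase. If it omits subjects because an insertion complication ended the procedure, that profile looks better than it was. Safety results to one month are part of the planned submission to the NMPA (Protocol 3.2), so a planned table with this gap is worth correcting.

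**Working it through.** **1. Set membership under SAP 6**

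| Subject | SAF | FAS | Run-in set |
|---|---|---|---|
| Main phase, power delivered | yes | yes | no |
| Main phase, stopped after puncture, before power | yes, if an attempt includes puncture | no | no |
| Run-in, power delivered | yes | no | yes |
| Run-in, stopped after puncture, before power | yes, same condition | no | yes, if counted as having entered run-in |

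The second row is the gap: FAS plus run-in set can fall short of the SAF by exactly these subjects. A stop after power has started is classed as an A2 ablation (Protocol 7.2.3) and stays in the FAS, so only stops before power matter. Splitting the safety set into run-in and the rest, as Protocol 8.1 describes, would leave no such gap.

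**2. Denominator**

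The plan's main-phase sample size reproduces. With P0 = 0.80, P1 = 0.90, one-sided 0.025 and 80% power:

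n = [(1.960 × √(0.8 × 0.2) + 0.842 × √(0.9 × 0.1)) / 0.10]² = 107.43, rounded up to 108; 108 / 0.90 = 120.

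I take the FAS as 120, because subjects stopped before power are replaced.

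**3. Size of the effect**

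The documents give no number of stops, so k is an assumption. Let x be the FAS subjects with the AE, and assume first that every stopped subject had it.

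- Rate shown: x / 120
- Rate among attempted main-phase procedures: (x + k) / (120 + k)
- Difference: [k / (120 + k)] × (1 − x / 120)

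| Rate shown on the FAS | k = 1 | k = 2 | k = 4 | k = 6 |
|---|---|---|---|---|
| 0/120 = 0.0% | 0.8% | 1.6% | 3.2% | 4.8% |
| 6/120 = 5.0% | 5.8% | 6.6% | 8.1% | 9.5% |
| 12/120 = 10.0% | 10.7% | 11.5% | 12.9% | 14.3% |
| 24/120 = 20.0% | 20.7% | 21.3% | 22.6% | 23.8% |

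Over this grid the difference runs from 0.7 points (24/120, k = 1) to 4.8 points (0/120, k = 6). At a FAS rate of 30% a single stop adds 0.6 points. With k = 0 the difference is zero.

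**4. Direction**

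If only j of the k stopped subjects had the AE, the attempted rate is (x + j) / (120 + k). It exceeds the FAS rate when j/k is greater than x/120. That is to be expected for the complication that caused the stop, but not for every AE: with x = 24, k = 6 and j = 0 the attempted rate is 24/126 = 19.0%, below the 20.0% shown.

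**The case against.** The strongest reply is that nothing is lost from the report. The SAF is the main safety population in SAP 6 and 8.10.7, the FAS and run-in summaries are extras, and SAP 8.1 lists all SAF subjects sorted by stage. The stopped subjects' events appear in the SAF tables and, by phase, in the listings. This stands and limits the point to a supplementary table. It does not remove it. Listings give no rate, and subtracting the run-in table from the SAF table works only if every member of the run-in set is in the SAF, which the definitions do not guarantee.

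Four stronger readings are tempting, and the documents do not support them.

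- **That an apparent fall in complications after run-in would be an artefact.** Neither document plans a run-in versus main-phase comparison. Separate run-in summaries are only permitted in Protocol 8.1 and 8.7, and SAP 6 does not present the two sets as a partition of the SAF.
- **That chest-tube pneumothorax or treated hemorrhage will be shown understated.** SAP 8.10.7 describes the predefined AEs in a section performed on the SAF and extends only the AE summary to the other sets. Whether that breakdown is repeated on the FAS is not clear from the text.
- **That the run-in denominator is inflated by subjects never punctured.** Protocol 7.2.3 makes subjects excluded before puncture screening failures, and the run-in is described as subjects treated. What remains, such as withdrawal between enrolment and ablation, is narrow. The same wording leaves some doubt whether a run-in subject stopped before power counts as having entered the run-in.
- **That the understatement is large.** Any multiple depends entirely on the stop and event counts assumed, and stops are also allowed for reasons other than AEs.

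**Conclusion.** The point holds in a limited form and is minor. By the SAP's definitions, the only AE summary planned in the SAP text without run-in subjects omits main-phase subjects stopped between puncture and power. It is therefore too low for the complications that cause such stops, and the FAS and run-in tables need not add up to the SAF. The 0.7 to 4.8 point range is an illustration that rests on a FAS of 120, FAS rates from 0% to 20%, 1 to 6 stops, and the event in every stopped subject.

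A reader might infer that insertion complications vanish from the safety evaluation. They do not: the primary safety analysis on the SAF is unaffected, provided that an attempt is taken to begin at puncture. SAP 6 does not say so, and on a narrower reading these subjects would leave the SAF as well.

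The FAS wording in Protocol 8.7 is a related inconsistency. Taken literally, it would drop the same subjects from the primary safety analysis. The SAP states that it supersedes the protocol's statistical section where they differ, so this adds no weight to the present point, but the texts should agree.

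**What to change.** 1. In SAP 6 and 8.10.7, replace the FAS and run-in set for the additional AE summaries with two parts of the SAF: non run-in subjects and run-in subjects. Both phases then follow the attempted-ablation rule, and the two tables add up to the SAF.
2. In the SAF definition, state that an attempt starts at probe puncture on the skin, which is where Protocol 7.1.8 starts AE reporting.
3. Reconcile Protocol 8.7 with Protocol 8.1 and SAP 6, so that all three name the safety set for the primary safety analysis.

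The cost is a short text change and a population flag derived from data already collected. The primary endpoint and its success criterion are untouched. The downside is that the stated main-phase complication rates may become slightly less favourable.
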